Descriptive statistics of qualitative variables in the study will be given as number and percentage, and descriptive statistics of quantitative variables will be given as mean, median, standard deviation, minimum and maximum. Pearson chi-square and Fisher's exact chi-square tests will be used to compare the distribution of the relevant variables between the groups. The conformity of quantitative variables to normal distribution will be examined by Shapiro Wilk test. For normally distributed variables, one-way analysis of variance will be used to compare the means of more than two groups. Tukey test will be used as a posthoc test for pairwise comparisons. For non-normally distributed variables, Kruskall Wallis test will be used in the mean comparison of more than two groups and pairwise comparisons will be examined with Dunn test. Paired t test will be used for the mean comparison of two dependent groups and Wilcoxon signed-rank test will be used for median comparisons. Repeated measures analysis of variance method will be used for mean comparisons of more than two dependent groups and Friedman test will be used for median comparisons. Statistical significance level will be taken as 0.05 and SPSS (Version 28) package program will be used for calculations. For the gastric volume value, at the 95% confidence level, when the significance of a mean difference of 18.18 with 80% power is attributed (means 67.22 and 49.04 with standard deviations 29.49 and 15.4), a minimum of 28 people should be included in the study in each group. [1] Therefore, we planned the number of patients in the study groups as 30 for each group. 1

Inclusion Criteria:

1. Between the ages of 18-65
2. Elective laparoscopic cholecystectomy planned under general anesthesia
3. American Society of Anesthesiologists (ASA) class I-II physical condition

[figure not shown]
Exclusion Criteria:

1. Patients with gastroesophageal reflux and gastrointestinal motility disorders
2. diabetes mellitus
3. Mental retardation, previous neurological disease symptoms (syncope, dementia, alzheimer etc.)
4. Chronic alcoholism
5. Difficult Intubation
6. Patients with ASA physical status classes \geq III
7. Patients with a body mass index of 35 and above
8. History of meniere and motion sickness
9. Presence of previous history of postoperative nausea and vomiting
10. Smoking

Numerik Rank Score:

0: no vomiting or nausea
1: nausea
2: nausea and once vomiting
3: twice or more vomiting

VAS:

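### No T0-adjusted comparison of the groups is named for glucose, insulin, cortisol or the comfort VAS, although T0 is collected for all of them

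*Combined protocol and SAP*

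**What the plan says.** Section 3 (Method) has glucose, insulin and cortisol measured at T0 (two hours before the operation), T1 (before induction) and T3 (two hours after surgery). Thirst, hunger, dry mouth and fatigue are scored by VAS at T0 and T1. The follow-up form has a matching row at two hours before surgery, with VAS, glucose, insulin and cortisol columns.

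The statistical analysis paragraph is a general list of tests, not tied to named outcomes. For quantitative variables it gives:

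- **Between groups, normal data:** "one-way analysis of variance will be used to compare the means of more than two groups", and "Tukey test will be used as a posthoc test for pairwise comparisons".
- **Between groups, non-normal data:** "Kruskall Wallis test will be used in the mean comparison of more than two groups", and "pairwise comparisons will be examined with Dunn test".
- **Two dependent measurements:** "Paired t test will be used for the mean comparison of two dependent groups", with Wilcoxon signed-rank as the alternative.
- **More than two dependent measurements:** "Repeated measures analysis of variance method will be used for mean comparisons of more than two dependent groups", with Friedman as the alternative.

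It names no covariate, no between-group comparison of change, no mixed model and no group-by-time term.

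**The concern.** Tests within a group show whether that group changed over time. They do not show whether the groups differ. The tests that do compare groups ignore T0. So no planned analysis is said to estimate the group difference at T1 or T3 given where patients started.

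Stress response is one of the three effects in the official title, and the three blood measures appear to be its markers, though the plan does not say so. The sample size was set on gastric volume, so nothing in the plan secures power for these outcomes. Using a baseline that is already collected is a way to gain precision without more patients. It also removes the part of a chance T0 difference that carries through to follow-up.

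**Working it through.** **Inputs from the plan.** Three groups; "we planned the number of patients in the study groups as 30 for each group"; 109 patients reported as included (109/3 = 36.3, so about 36 per group if split equally); significance level 0.05, taken as two-sided.

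**Assumed, because the documents give no value.** T0-to-follow-up correlation ρ = 0.2, 0.3, 0.5 or 0.7; true pairwise difference 0.6 SD; equal variances; a common slope on T0; random allocation.

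**Step 1: the plan's own figure.** The 28 per group rests on gastric volume means of 67.22 and 49.04 with SDs 29.49 and 15.4.

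- Pooled SD = √[(29.49² + 15.4²)/2] = 23.52.
- Normal approximation: n = 2 × [23.52 × (1.960 + 0.842)/18.18]² = 26.3, so 27.
- Noncentral t: power is 79.6% at 27 and 81.1% at 28.

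The 28 reproduces. Section 3 describes gastric volume only at T1, so the present point does not touch it.

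**Step 2: power with and without T0.** Adjustment multiplies the residual variance by 1 − ρ². For one pair:

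- SE = √[2(1 − ρ²)/n] in SD units; noncentrality δ = 0.6/SE.
- Critical value = Tukey studentized range (3 groups)/√2, with 3n − 3 degrees of freedom unadjusted and 3n − 4 adjusted. At n = 30 it is 2.38 in both cases.
- Example, n = 30: unadjusted δ = 0.6/√(2/30) = 2.32, power 47.9%. At ρ = 0.5, δ = 0.6/√(2 × 0.75/30) = 2.68, power 61.8%.

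| Tukey pairwise power | Unadjusted | ρ = 0.2 | ρ = 0.3 | ρ = 0.5 | ρ = 0.7 |
|---|---|---|---|---|---|
| Variance factor 1 − ρ² | 1 | 0.96 | 0.91 | 0.75 | 0.51 |
| 30 per group | 47.9% | 49.8% | 52.3% | 61.8% | 80.6% |
| 36 per group | 56.8% | 58.8% | 61.5% | 71.2% | 88.0% |

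Simulating the ANCOVA with random T0 values gives 48.9, 51.6, 61.1 and 79.9% at 30 per group, with family-wise error of 5.0–5.3% under the null.

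**Step 3: unequal slopes.** If T0 predicts follow-up in two groups but not in the third (ρ = 0.5/0.5/0 or 0.7/0.7/0), power for the third group against another rises from about 48% to only 53% or 59% at 30 per group. Family-wise error stays at 5.0% and 5.3%.

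**Step 4: chance imbalance at T0.** At 30 per group the SE of a T0 difference is √(2/30) = 0.258 SD. A gap of 0.5 SD is 0.5/0.258 = 1.94 SE. It has a 5.3% chance for a named pair and about 12.8% for at least one of the three pairs on a given measure. Such a gap moves the unadjusted follow-up difference by ρ × 0.5, that is 0.10, 0.15, 0.25 or 0.35 SD.

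Simulated family-wise error of the planned Tukey comparisons, with T0 sample means held at the stated gap (40,000 runs per cell, simulation SE 0.11–0.17 points in the 0.5 SD rows):

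| T0 gap, position of third group | ρ = 0.2 | ρ = 0.3 | ρ = 0.5 | ρ = 0.7 |
|---|---|---|---|---|
| 0.5 SD, midway | 5.5% | 6.0% | 7.8% | 9.3% |
| 0.5 SD, level with one of the two | 5.9% | 6.7% | 10.2% | 14.0% |
| 0.174 SD (median, named pair), midway | 4.5% | 4.1% | 2.3% | 0.9% |
| 0.290 SD (median, largest pair), midway | 4.8% | 4.6% | 3.9% | 2.1% |

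The median for a named pair is 0.6745 × 0.258 = 0.174 SD. Kruskal-Wallis behaves much the same at 0.5 SD: 5.3, 5.9, 7.5, 8.8% midway and 5.7, 6.6, 9.7, 13.7% level. At typical imbalances the error is below 5%, because the unadjusted variance is then larger than it need be. Averaged over random allocation, one-way ANOVA simulates at 4.8–4.9%.

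**The case against.** The strongest reply is that nothing planned is invalid. Under random allocation one-way ANOVA holds its error rate, and choosing it over ANCOVA is a legitimate if less efficient choice. The size of the loss also rests on a correlation and an effect that the documents do not give. At ρ of 0.2–0.3 the gain at 30 per group is only two to four percentage points. A high correlation with a common slope cannot be presumed: glucose and insulin at T1 follow a carbohydrate drink in one group only, and T3 follows surgery. The comparison of most interest may therefore gain least. The raised error rates need an unusual T0 gap together with a high correlation. All of this stands, and it limits the point to efficiency.

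A second reply is that repeated measures ANOVA suits three time points and can carry a group factor. The plan states no such factor. Comfort VAS has only two time points, which leads to paired tests, and skewed measures go to Friedman. Even a group-by-time test would not be a T0-adjusted comparison. So this softens the point without removing it.

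Third, the remedy depends on facts not in the text. T0 and the drink share the same nominal time with no order given. Allocation is described only as a division into groups. Section 3 is written in the past tense, so data may already exist. These are real limits on the remedy, but they do not supply the missing analysis.

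**Conclusion.** The concern holds. T0 is available for glucose, insulin, cortisol and the comfort VAS, and no stated between-group comparison uses it. Under random allocation the cost is precision: pairwise power of 48% against 50–81% at 30 per group, and 57% against 59–88% at 36, for a 0.6 SD difference and ρ from 0.2 to 0.7. Below ρ of about 0.5 the gain is small. There is no general inflation of error; a near-extreme 0.5 SD T0 gap takes family-wise error to about 5.5–14.0%, depending on ρ and the third group.

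If allocation was not random, T0 differences could be systematic and adjusting for T0 alone would not secure the comparison. T0 is a valid baseline covariate only where it was taken before the drink. The change should be made because it is specific and nearly free; it is not a condition for the planned tests to be valid.

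**What to change.** - For the blood measures at T1 and T3, and the comfort VAS at T1, name an ANCOVA with group as factor and the T0 value as covariate, on a log or rank scale where data are skewed.
- Report Tukey-type adjusted pairwise differences with 95% confidence intervals, and check whether the T0 slope differs between groups.
- State whether T0 was taken before the drink. Do not use T0 as a covariate for any measure where that cannot be confirmed.
- If outcomes have already been seen, report the adjusted analysis as post hoc.

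The cost is SAP wording and a check of the T0 timing. No new data are needed. Each model loses one degree of freedom, or three if separate slopes are fitted.

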STUDY PROTOCOL

1. Date: 01.01.2023

2. Official Title:

THE EFFECT OF A NEWLY FORMULATED PREOPERATIVE ORAL CARBONHYDRATE SOLUTION ON GASTRIC EMPTYING, POSTOPERATIVE NAUSEA AND VOMITING AND STRESS RESPONSE

3. Method:

109 patients who underwent elective laparoscopic cholecystectomy, aged 18-65 years and ASA physical state 1-2 were included in the study. The patients were divided into 3 groups: Group A, who would not eat anything 6-8 hours before the operation, Group S, who drank 400 ml of water 2 hours before the operation, and Group K, which drank 400 ml preoperative oral carbohydrate solution (PreOKH) 2 hours before the operation. Before induction of anesthesia (T1), patients antral gastric cross-sectional area (GKA) and gastric volume (GV) were evaluated by gastric ultrasound. The preoperative anxiety level of the patients was determined by the State-Trait Anxiety Inventory (STA1) before the operation (T1), and the symptoms affecting the preoperative patient comfort parameters (thirst, hunger, dry mouth, fatigue) were measured 2 hours before the operation (T0) and before the induction (T1) evaluated with the visual analog scale (VAS). Postoperative nausea and vomiting (PONV) and postoperative pain levels were recorded. Blood glucose, insulin and cortisol levels of the patients were measured 2 hours before the operation (T0), before induction (T1) and postoperative 2nd hour (T3).

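### The 28 per group (30 planned) is sized for one unadjusted two-group t-test; for the plan's own three-group Tukey comparison, power at a common SD is about 69% and 73%, not 80%.

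*Combined protocol and SAP*

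**What the plan says.** The statistical paragraph of section 3 (Method) sizes the trial on gastric volume. The inputs are two means, 67.22 and 49.04, with SDs 29.49 and 15.4, a power of 80%, and an error level introduced by "For the gastric volume value, at the 95% confidence level". The result is that "a minimum of 28 people should be included in the study in each group". The paragraph continues: "Therefore, we planned the number of patients in the study groups as 30 for each group".

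The design has three arms (fasting, water, carbohydrate solution): "The patients were divided into 3 groups". For normally distributed variables the overall test is a one-way ANOVA, and "Tukey test will be used as a posthoc test for pairwise comparisons". For other variables it is Kruskal-Wallis, and "pairwise comparisons will be examined with Dunn test"; whether the Dunn p-values are adjusted is not stated. The general rule is "Statistical significance level will be taken as 0.05".

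The opening of section 3 refers to "109 patients who underwent elective laparoscopic cholecystectomy" as included. It gives neither the group sizes nor the number analysed. The plan does not name a primary pair of groups or say which pair the 18.18 stands for.

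**The concern.** The sample size uses two means and two SDs, as for a two-arm trial. The analysis compares three arms, and its pairwise test controls the error rate over all three pairs. Tukey's test needs a larger observed difference than a lone t-test does, so a size that just reaches 80% for the t-test must fall short of 80% for Tukey at the same SD and difference.

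This matters because it is the only power statement in the plan, and it concerns gastric volume, the measure behind the gastric-emptying aim in the title. A non-significant Tukey result, for example carbohydrate against water or carbohydrate against fasting, would be read as coming from a test with a 20% chance of missing a difference of 18.18. At the stated sizes that chance is higher.

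**Working it through.** **Inputs from section 3.** Difference 67.22 − 49.04 = 18.18; SDs 29.49 and 15.4; significance level 0.05 (taken as two-sided, because a one-sided normal calculation gives 21 and does not reproduce the plan); 28 per group as minimum, 30 planned; three groups.

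**Step 1: reproduce the 28.**

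Common SD = √[(29.49² + 15.4²)/2] = √[(869.66 + 237.16)/2] = √553.41 = 23.52. Standardised difference = 18.18/23.52 = 0.773.

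For a two-sample t-test with n per group, the noncentrality is 0.773 × √(n/2) on 2n − 2 degrees of freedom:

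| n per group | Noncentrality | Power, unadjusted t-test |
|---|---|---|
| 27 | 2.84 | 79.6% |
| 28 | 2.89 | 81.05% |
| 30 | 2.99 | 83.7% |

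The first n to reach 80% is 28, so the plan's figure is reproduced.

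**Step 2: power of the planned Tukey comparison.**

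The noncentrality is the same, but the error variance has 3n − 3 degrees of freedom and the critical value is q(0.95; 3, 3n − 3)/√2. At n = 28 this is 2.388, against 2.005 for the t-test.

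| n per group | Tukey critical value | Noncentrality | Power |
|---|---|---|---|
| 28 | 2.388 | 2.89 | 69.2% |
| 30 | 2.384 | 2.99 | 72.8% |
| 34 | – | 3.19 | 78.9% |
| 35 | – | 3.23 | 80.2% |
| 36 | 2.377 | 3.28 | 81.5% |

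So 80% needs 35 per group, or 3 × 35 = 105 in all. The chance of missing 18.18 is 1 − 0.692 = 31% at 28 and 1 − 0.728 = 27% at 30.

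**Step 3: the unknown third SD.**

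Tukey's test pools the variance over all three groups, and the plan gives no SD for the third. If it is 29.49, the pooled SD is √[(869.66 + 237.16 + 869.66)/3] = 25.67. If it is 15.4, the pooled SD is √[(869.66 + 237.16 + 237.16)/3] = 21.17. Simulated power with these unequal SDs (100,000 trials per setting; the third mean, set at 49.04, 58.13 or 67.22, made almost no difference):

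| n per group | Third SD 29.49 | 23.52 | 15.4 |
|---|---|---|---|
| 28 | 61% | 69% | 77% |
| 30 | 65% | 73% | 80% |
| 36 | 75% | 81% | 87% |

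Requiring a significant ANOVA as well lowers power only slightly: with a third SD of 23.52, to 68–69% at 28 and 71–73% at 30.

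**Step 4: could the 80% refer to the overall ANOVA?**

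At SD 23.52 the noncentrality is n × Σ(mean − grand mean)²/SD². This is n × 0.597 × 2/3 if the third mean equals one of the stated means, and n × 0.597 × 1/2 if it lies midway (0.597 = 0.773²).

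| n per group | Third mean equal to a stated mean | Third mean midway |
|---|---|---|
| 28 | 84% | 72% |
| 30 | 87% | 75% |

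The stated inputs contain no third mean, so the 28 was not obtained this way.

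**Step 5: the Dunn route.**

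Simulation on normal data (20,000 trials per setting; third mean 49.04 to 67.22, third SD 15.4 to 29.49) gives 74–88% at 28 and 77–90% at 30 for unadjusted p-values, and 56–76% and 60–79% with a Bonferroni adjustment. These figures only illustrate the effect of adjustment: the plan uses Dunn when data are not normal, and power then depends on the shape of the distribution.

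**The case against.** The strongest objection is that the shortfall belongs to sizes the trial may not have. The 109 patients reported as included are about 36 per group if split evenly, and at 36 the Tukey power is about 81% at the common SD. This stands, and the finding is limited to the stated 28 and planned 30 because of it. It does not clear the plan. The split and the number analysed are not given, the 109 is not reconciled with 3 × 30 = 90, and with a third SD of 29.49 power at 36 is still 75%.

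Second, the 69% and 73% depend on an SD that the plan does not give, and with a third SD of 15.4 the planned 30 does reach about 80%. That is correct, and it is why the range belongs beside the point values. At 28, every value tried stays below 80%.

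Third, the 28 is not miscalculated, Tukey applies only to normally distributed variables, and the plan never says that the 80% holds for each Tukey pair. All true: the fault is a mismatch between the test used for sizing and the test used for analysis. Reading the 80% as overall ANOVA power helps only if the third mean lies near one of the other two, and a significant overall test does not show which groups differ.

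Fourth, Dunn figures simulated on normal data should not serve as the power of the non-normal route. Agreed. A check on skewed data with the same means and SDs gave lower unadjusted power at 30 per group: 74–85% for lognormal and 70–84% for gamma shapes. The shapes are assumptions, so no Dunn figure belongs in the restated power sentence.

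**Conclusion.** The concern holds. The only power statement in the plan describes one unadjusted comparison of two groups, while the plan tests three groups with a stricter pairwise procedure and names no primary pair. On the normal-data route, at the common SD, the stated minimum is 35 − 28 = 7 per group short of 80% power and the planned number 35 − 30 = 5 short.

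The size of the shortfall rests on the third group's SD, on the plan's own two means and SDs being right (the cited source was not checked), and on 28 or 30 patients per group being analysed. The mismatch should be corrected, but it does not invalidate the trial. It changes how a non-significant pairwise result on gastric volume may be read, and at about 36 analysed per group it would matter little. On the non-normal route, multiplicity reduces power only if the Dunn p-values are adjusted.

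**What to change.** **Option (a), open at any time.** Replace the power sentence with text to this effect:

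> With 28 per group, power is 81% for one unadjusted comparison of two groups. For the planned Tukey comparison it is about 69% with 28 and 73% with 30 per group, assuming a common SD of 23.52 (61–77% and 65–80% for a third-group SD between 29.49 and 15.4).

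Add the power at the number actually analysed in each group, explain how 30 per group became 109 in total, and state whether Dunn p-values are adjusted and by what method.

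**Option (b), only if gastric-volume results have not been seen.** Name the pair that the 18.18 represents as the single primary comparison, tested alone at 0.05, with the other two pairs secondary. The existing calculation then matches the analysis. Because the opening of section 3 is written in the past tense, the date of this choice relative to the data must be stated. If results have been seen, only option (a) remains.

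**Cost.** Two or three sentences and no extra patients. Option (a) makes the stated power look less favourable; option (b) gives two of the three pairwise comparisons secondary status.

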Qualitative evaluation of the antrum with gastric USG:

Grade 0: empty antrum both in the semi-sitting position and in the RLDP

Grade 1: gastric fluid is only visible in RLDP;

Grade 2: gastric fluid can be seen both in the semi-sitting position and in RLDP

Factor Loading

Item	I	II	h^2
1. I feel calm	.50	-.21	.41
2. I feel secure	.61	-.10	.45
3. I am tense	.01	.63	.39
4. I am strained	.05	.59	.32
5. I feel at ease	.59	-.05	.38
6. I feel upset	.03	.78	.58
7. I am presently worrying	-.01	.57	.33
8. I feel satisfied	.57	-.10	.39
9. I feel frightened	-.03	.69	.50
10. I feel comfortable	.59	-.19	.51
11. I feel self-confident	.70	.04	.46
12. I feel nervous	.05	.76	.54
13. I feel jittery	.01	.73	.52
14. I feel indecisive	-.09	.55	.37
15. I am relaxed	.58	-.10	.41
16. I feel content	.62	.06	.35
17. I am worried	.12	.79	.54
18. I feel confused	-.10	.62	.45
19. I feel steady	.69	-.01	.47
20. I feel pleasant	.68	.05	.43
21. I feel pleasant	.64	.02	.40
22. I tire nervous and restless	-.32	.44	.44
23. I feel satisfied with myself	.79	.09	.56
24. I wish I could be as happy as others seem	-.20	.23	.14
25. I feel like a failure	-.48	.15	.32
26. I feel rested	.61	.09	.33
27. I am calm, cool, and collected	.67	.03	.43
28. I feel that difficulties are piling...	-.34	.38	.39
29. I worry too much over something...	-.06	.37	.16
30. I am happy	.70	-.05	.52
31. I am inclined to take things hard	-.20	.38	.27
32. I lack self-confidence	-.38	.17	.25
33. I have disturbing thoughts	.78	.03	.59
34. I make decisions easily	.50	.02	.27
35. I feel inadequate	-.38	.21	.27
36. I am content	.70	-.07	.55
37. Some unimportant thought runs...	-.10	.34	.16
38. I take disappointments so keenly...	-.26	.28	.22
39. I am a steady person	.52	-.08	.32
40. I get in a state of tension or turmoil...	-.38	.30	.35

Note. Interfactor correlation = -0.52. Factor loadings are standardized regression coeff

FOLLOW-UP FORM

No:		Duration of operation	
Age-gender		Fasting time	
BMI		Anesthetic agent consumption	Sevoflurane: Remifentanil:
GRUP			
ASA		complications:	
disease		Antiemetic need :	

Gastric examination

Gastrik USG – measurement of CSA in RLPD (CSA = (LD × SD × π)/4)	LD:	SD:	CSA:
Gastric volume (GV = 27,0 + 14,6 × CSA (RLDP'de) – 1,28 × age)			
Qualitative evaluation score			
Gastiric volume (aspiration of ngs)			
Gastric pH			

Intraoperative vital sing

	HR	SP/DP	MAP	SpO ₂	BIS
Before induction					
İnd +1. min					
10. min					
20. min					
30. min					
40. min					
50. min					
60. min					

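### Ultrasound gastric volume has age in its formula and age is recorded, but no comparison adjusts for it: a cheap, optional precision gain of uncertain size, not an error

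*Combined protocol and SAP*

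**What the plan says.** All references are to the combined protocol and SAP.

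- **Follow-up form, Gastric examination.** Ultrasound volume is derived as "GV = 27,0 + 14,6 × CSA (RLDP'de) – 1,28 × age". Age has its own field on the form. A second volume, "Gastiric volume (aspiration of ngs)", has no age term.
- **Section 3, Method.** Before induction (T1), "antral gastric cross-sectional area (GKA) and gastric volume (GV) were evaluated by gastric ultrasound". The planned tests therefore read as applying to both measures.
- **Section 3, statistical paragraph.** For normally distributed variables, "one-way analysis of variance will be used to compare the means of more than two groups", and "Tukey test will be used as a posthoc test for pairwise comparisons". Variables that fail Shapiro-Wilk go to Kruskal-Wallis and Dunn. No ANCOVA, regression or other adjusted comparison is listed.
- **Section 3, sample size.** The calculation is for gastric volume, using "means 67.22 and 49.04 with standard deviations 29.49 and 15.4", which gives at least 28 per group; "we planned the number of patients in the study groups as 30 for each group". It does not say whether ultrasound or aspirated volume is meant. Ultrasound volume appears to be the intended one.
- **Section 3, opening.** "109 patients who underwent elective laparoscopic cholecystectomy, aged 18-65 years and ASA physical state 1-2 were included in the study". The text says the patients were divided into three groups and does not say how.

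**The concern.** Age enters the apparent sizing outcome by construction and is already collected. Any age scatter in GV that is not offset by a relation between CSA and age stays in the error term of an unadjusted comparison, where it widens the confidence interval.

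There is a second consequence. GV is a linear function of CSA and age, so unadjusted GV and unadjusted CSA are two tests of one measurement that differ only by an age term. They can disagree on significance. Which of them is more precise depends on a CSA-age slope that the documents do not give. At stake are some precision on the outcome that sizes the trial and a clear statement of which result decides.

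**Working it through.** **1. The plan's own figure.** The difference is 67.22 - 49.04 = 18.18. The pooled SD is sqrt((29.49² + 15.4²)/2) = 23.52. With two-sided alpha 0.05 (sidedness is not stated) and 80% power, the two-sample t test needs 27.3, rounded up to 28 per group. The Welch test gives power 0.791 at 27 and 0.806 at 28. The stated 28 reproduces. At 30 per group the t test has power 0.837.

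**2. The net age slope.** If CSA changes by b cm² per year of age within a group, GV changes by 14.6b - 1.28 mL per year. This is -1.28 if b = 0 and zero if b = 1.28/14.6 = 0.088 cm² per year. The documents do not give b.

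**3. Adjusted GV and adjusted CSA are one test.** Write CSA = a + τ·group + β·age + e. Substituting into the form's formula gives

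GV = (27.0 + 14.6a) + 14.6τ·group + (14.6β - 1.28)·age + 14.6e.

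The group effect and the residual are both multiplied by 14.6, so the t statistic and p-value are identical. This needs no assumption about age.

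**4. Size of the gain.** Three things are assumed: an age SD of 8-10 years (not in the documents), the planning SDs applying to this formula (the documents do not say that the cited study used it), and normal data. Total GV SDs were held at 29.49 and 15.4, with 40,000 simulated trials per cell, 30 per group and a single pair at 0.05. Ranges run over age SD 8 and 10.

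| CSA-age relation | Unadjusted GV | Unadjusted CSA | Age-adjusted | Mean 95% CI half-width, unadjusted GV to adjusted (mL) |
|---|---|---|---|---|
| None (b = 0) | 84% | 90-94% | 90-93% | 12.1 to 11.0-10.2 |
| Half offset | 84% | 84% | 85-86% | 12.1 to 11.9-11.7 |
| Full offset (b = 0.088) | 84% | 73-77% | 83% | 12.1 to 12.2 |

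A separate run put the lower end of the half-offset row at 84%, so 84-86% is the fair range. The type I error of the adjusted test was 0.049-0.053. Tukey control over three groups lowers power with or without age. That comes from the multiplicity threshold and the third group's SD, not from age.

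**5. Why the first row is an upper bound.** With b = 0, mean GV would fall by 1.28 × 47 = 60.2 mL between ages 18 and 65, against planning means of 49.04 and 67.22. Age would account for (1.28 × 8)²/15.4² = 44% to (1.28 × 10)²/15.4² = 69% of the variance in the group with SD 15.4. The case becomes impossible once the age SD exceeds 15.4/1.28 = 12.0 years.

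**6. Disagreement between results.** With a true 18.18 mL difference, unadjusted GV and unadjusted CSA disagree on significance in 8-15% of simulated trials. With no difference, at least one of them is significant in 7-8%.

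**7. If the 109 patients are the analysed set.** At about 36 per group, unadjusted GV power is 90%. Adjusted power is 94-97%, 91% and 89-90% in the three rows.

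**The case against.** The strongest reply is that nothing is broken. One-way ANOVA without covariates is a legitimate choice, the sample size reproduces and the stated power is met. The only sizeable gain comes from the case that the planning SD makes least credible. If the age term exists to correct antral area for age, GV already has the age effect removed and nil gain is the natural expectation. All of this stands, and it is why the point is optional.

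Two further objections shape the remedy. Adding an ANCOVA beside the unadjusted test without saying which decides would keep results that can disagree: adjusted and unadjusted GV differ on significance in 2-12% of simulated trials with a true difference, and under no difference one or the other is significant in 5-8%. An unconditional ANCOVA would also conflict with the plan's switch to Kruskal-Wallis for non-normal variables. Both are right, and the fix has to settle both.

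A reader might infer that the formula adds 1.28 mL of noise per year, so that adjustment must help. It does not follow, because -1.28 is the slope at fixed CSA. A reader might also infer that the unadjusted comparison is biased by age. At fixed CSA, a 5-year gap in mean age would shift GV by 1.28 × 5 = 6.4 mL, 35% of 18.18. But the documents neither report such a gap nor say that allocation was not random.

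**Conclusion.** The point holds as a suggestion to consider. Age is in the GV formula, it is on the form, and no planned comparison uses it. Under the assumptions above, adjustment moves single-pair power at 30 per group from about 84% to somewhere between 83% and 86%, with 90-93% as an unlikely ceiling. In every case examined, the adjusted test is within about 1 point of the better of the two unadjusted tests, or above both. The trial therefore need not guess which unadjusted measure is the more precise.

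The documents do not support reading this as a power shortfall or an invalid analysis. The size of the gain rests on an age SD and a CSA-age slope that they do not give, on planning SDs that may come from a different formula, and on ultrasound GV being the sizing outcome. It does not extend to the aspirated volume. Validity of the unadjusted test rests on random allocation, which the text does not state.

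**What to change.** Add to the statistical paragraph, for T1 ultrasound GV only:

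- The deciding comparison is an ANCOVA with group as factor and age in years as a continuous covariate. Adjusted pairwise differences are given with 95% CIs under Tukey-type control.
- For this outcome, normality is checked on the model residuals, with a rank-based ANCOVA if they are clearly non-normal. This replaces the Shapiro-Wilk/Kruskal-Wallis switch.
- Age-adjusted CSA is the same test and is reported as the same result. Unadjusted GV and CSA comparisons are supportive and do not decide significance.

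Section 3 opens in the past tense. If analysis has already begun, label the model as added later.

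The cost is a few SAP lines and one degree of freedom, with no new data and no extra patients. The gain may be nil, and up to about 1 point of power is lost if CSA fully offsets the age term.
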